3 months (+/- three weeks)- Follow-up	OHIP-49 BPI questionnaire PGIC Scale Rationale: We expect an immediate elimination of pain but the impact on OHRQL will be more quantifiable if assessed over time.	OHIP-49 BPI questionnaire PGIC Scale Rationale: We expect an immediate elimination of pain but the impact on OHRQL will be more quantifiable if assessed over time.

Data Collection Procedures

Initially patients will be consented for enrollment and treatment in the study. Data for the clinical study will be collected multiple times during the study including prior to treatment, and 1 week, 2 weeks, and 3 months post treatment. Patients will receive an OHIP-49 questionnaire and a modified BPI and the third survey (PGIC scale) to relate to overall oral health via electronic emails. The surveys will be emailed to the participants via a secure survey source (REDCap) and completed electronically by the participants after their initial visit for the restoration placement. Patients will have 7 days to complete the email surveys and email reminders will be sent daily until the surveys are completed. If patients are unable to complete an emailed survey, they have the opportunity to return to the school to complete the surveys. The UMSoD has a supply of iPads® available for research purposes and will be used to collect data at the initial enrollment and if patients come to the school to fill out follow up surveys. There will be a 3-week window for subjects to return to the school for the 3-month follow-up visit.

Data management

All scanned data that goes to a digital form and acquired digital data will be kept on a secure server at the University of Michigan School of Dentistry that is password protected. A secure patient treatment record will be created with the patients assigned participant number, all paper materials returned from patients and participant consent materials will be kept in a locked cabinet in a locked office at the University of Michigan School of Dentistry..

Statistical Analysis Plan

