Prior to testing primary study aims, we will examine data distribution characteristics to identify outliers and determine suitability of the data for parametric testing. Bivariate correlations will be conducted to identify important covariates for inclusion in main statistical models (e.g. age). Assuming underlying assumptions are met, we will use repeated measures of general linear models (GLM) to test for significant differences between the control and treatment groups in terms of changes in pain (specific aim 1) and oral health related quality of life (specific aim 2) over the course of the study. Significant group versus time effects will be examined graphically to determine the nature of the interaction and to qualify how pain and oral health related quality of life changed over time for each group.

Power Analyses

Currently, we do not have input data available to do an adequate sample size analysis or the study. For this small pilot study, we planned for a sample of 40 participants (20 subjects in control group and 20 in the experimental group) to generate some preliminary data for conducting a rigorous sample size analysis for a larger clinical trial

Potential Problems and Alternatives Strategies

In the event that we do not recruit enough patients to fulfill project timeline, we can recruit patients from the graduate clinic at the University of Michigan School of Dentistry and the emergency clinics.

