1.4.2. Psychological. Participants will be asked to provide information about their self-reported pain associated with tooth sensitivity and to answer the OHIP-49 questionnaire, BPI survey and PGIC survey. These questions have a small likelihood of low psychological risk. If participants demonstrate to be uncomfortable or emotionally disturbed by the questionnaires, they will be reminded that there is absolutely no obligation to fulfill the questionnaires. In these cases, the patients will still receive the dental care proposed in this study.

2. Protection Against Risks

2.1. Recruitment and informed consent. For recruitment, we will distribute flyers at the UMSoD and we will send emails to the dental students (dental providers) about information on the study. Volunteers who are

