interested in an alternative treatment for tooth sensitivity will be examined per the guidelines of the UMSoD, informed about the study and take a pre-screen questionnaire. After selecting the volunteers under the inclusion and exclusion criteria, patients will receive a random number at the study enrollment session. From this point on, we will only identify the patients by the given enrollment random number and age. A well-trained team of third and fourth-year dental students will deliver the dental care including the restorations in the Foundations Clinic at the UMSoD and will be supervised by [name] and [name]. The dental care treatments proposed in this study are part of the second year dental students competency requirement. We strongly believe that the third and fourth year dental students are entirely competent to delivery such treatments based on the competencies they passed in their first and second years of their dental training. A second team of dental students that are blinded to the treatment will collect and analyze the data at the designated time points. Prior to conducting any treatment and assessing the self-perceived outcomes, all participants will be given a formal Statement of Consent Form to read. The interviewer will verbally explain the form by the following study team members: [name] or [name] and the study coordinator, [name], if necessary. Participants will sign the form indicating that they understand that they are being asked to participate in a research study, that they understand the risks involved in participating, that they can refuse to answer any question that they are not comfortable with, and that the information they provide will be kept strictly confidential. The informed consent form will also provide assurances that their participation in the research aspect of this project will in no way affect their patient status either positively or negatively.

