2.2. Protection against risks

2.2.1. Minimizing physical and psychological risks. Participants are free to refuse to respond to any question that may result in psychological disturbance. Written information collected is for research purposes only and will not become part of their personnel chart records. Individual responses to our questionnaires will not be linked to identifying information, except for age, and will not at all influence current or future delivery of dental care at the UMSoD. These precautions are expected to effectively eliminate risks associated with the study participation. Management of complications of epinephrine and systemic medications, such as propranolol, will be mitigated by allowing participants to receive a maximum of two carpules of 2% lidocaine HCl containing 1:100,000 of epinephrine which is well within the recommended dose for epinephrine and patients with cardiovascular complications.

2.2.2. Minimizing risks to confidentiality. Identifying information from any of the participants in the study will be kept separately from the forms on which they record their responses to the questions. The participants identifying information will be safely stored at the University of Michigan Mident Axium system as any other patient assisted at the UMSoD. Records will be linked to individuals only through the enrollment number and the information used to link records with identifying information will be kept in a securely file drawer in a locked room only accessible to project principal investigators. Names and any other identifying information collected will be kept in a locked file drawer in a locked room only accessible to the project principal investigators and study coordinator. References to names or other identifying information will be eliminated from the written transcript of the interview in preparation for analysis of qualitative data. Names and any other identifying information will be eliminated in preparation for analysis of these records. These are precautions that we expect to be completely effective in eliminating risks to confidentiality. Email identifiers in the surveys will also be eliminated during analysis of the study.

3. Potential Benefits

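### The SAP names a repeated-measures GLM over four surveys with no missing-data rule; in its usual complete-case form it drops anyone who misses one survey

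*Combined protocol and SAP*

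**What the plan says.** The Statistical Analysis Plan gives one method for pain (aim 1) and oral health related quality of life (aim 2): "Assuming underlying assumptions are met, we will use repeated measures of general linear models (GLM". It adds that "Significant group versus time effects will be examined graphically to determine the nature of the interaction". It also covers outliers, suitability for parametric testing and choice of covariates. Nothing in the document mentions missing data, imputation, dropout, an analysis population, a mixed model or a sensitivity analysis.

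OHIP-49 and the modified BPI are taken at four time points (Table 2; Data Collection Procedures). For the emailed follow-ups, "Patients will have 7 days to complete the email surveys and email reminders will be sent daily until the surveys are completed", and "If patients are unable to complete an emailed survey, they have the opportunity to return to the school to complete the surveys".

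Protection of Human Subjects allows surveys and items to go unanswered:
- Section 1.4.2, on participants who are uncomfortable: "they will be reminded that there is absolutely no obligation to fulfill the questionnaires".
- Section 2.1, on consent: "that they can refuse to answer any question that they are not comfortable with".
- Section 2.2.1: "Participants are free to refuse to respond to any question that may result in psychological disturbance".

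The sample of 40 (20 per arm) is not derived from a calculation. Power Analyses gives its purpose as "to generate some preliminary data for conducting a rigorous sample size analysis for a larger clinical trial".

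**The concern.** A repeated-measures GLM in its multivariate or ANOVA form takes one row per person with all four scores present. Software then deletes a participant with any gap, including the surveys that person did return. The SAP neither chooses this form nor rules it out, so two analysts following the same text could analyse different people.

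The protocol itself allows gaps at two levels: a whole survey can be declined, and a single question can be refused. No rule says how an OHIP-49 or BPI with a blank item is scored, so one refused question could void a survey and, through listwise deletion, the participant.

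At stake are the precision of the treatment-effect estimate and, if completion depends on how people feel after treatment, its freedom from selection. No power is claimed, so no power is lost.

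**Working it through.** **Inputs from the documents.** N = 40, 20 per arm; one baseline and three follow-up surveys. No response rate, SD, effect size or alpha is given, so there is no stated calculation to reproduce.

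**Assumptions.** Baseline complete; response p per follow-up survey from 80% to 98%; correlation 0.5 between any two occasions with equal variances. Misses are independent (intraclass correlation, ICC, 0), partly clustered (beta-binomial, ICC 0.4) or fully clustered (ICC 1, the same people miss everything).

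**Step 1: complete cases.** Independent: 40 × p³. Fully clustered: 40 × p.
- 98%: 40 × 0.98³ = 37.6; 40 × 0.98 = 39.2
- 95%: 34.3; 38.0
- 90%: 29.2; 36.0
- 80%: 20.5; 32.0

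At ICC 0.4, with a + b = (1 − 0.4)/0.4 = 1.5 and a = 1.5p, P(all three answered) = a(a+1)(a+2)/(1.5 × 2.5 × 3.5). At 90% this is 1.35 × 2.35 × 3.35/13.125 = 0.810, or 32.4 people; at 80% it is 25.7.

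**Step 2: effect on the planned test.** The four-occasion group-by-time test has 3 df. I compare the expected information for the three change contrasts, taking the covariance as known. Equivalent complete participants = 40 × (det of the contrast covariance with full data / det with available data)^(1/3). For the month-3 change, the SD is √(2 × (1 − 0.5)) = 1, so the complete-case standard error is √(2/n per arm); at 90% independent, √(2/14.58) = 0.370.

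| Response, pattern | Equivalent N: complete-case vs all surveys | SE of month-3 change (SD units) | Baseline-adjusted SE (simulated, about ±0.01) |
|---|---|---|---|
| 98%, independent | 37.6 vs 39.2 | 0.326 vs 0.318 | 0.28 vs 0.27 |
| 95%, independent | 34.3 vs 38.1 | 0.342 vs 0.321 | 0.30 vs 0.28 |
| 95%, ICC 0.4 | 36.1 vs 38.2 | 0.333 vs 0.322 | – |
| 90%, ICC 1 | 36.0 vs 36.5 | 0.333 vs 0.329 | – |
| 90%, ICC 0.4 | 32.4 vs 36.3 | 0.351 vs 0.328 | 0.31 vs 0.30 |
| 90%, independent | 29.2 vs 36.2 | 0.370 vs 0.327 | 0.33 vs 0.29 |
| 80%, ICC 0.4 | 25.7 vs 32.6 | 0.394 vs 0.342 | 0.35 vs 0.31 |
| 80%, independent | 20.5 vs 32.4 | 0.442 vs 0.341 | 0.41 vs 0.31 |

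A correlation of 0.3 or 0.7 moves the equivalent N by at most 0.4.

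**Step 3: the SD, which the pilot needs most.** The coefficient of variation of a pooled SD is 1/√(2(n − 2)). At 90% independent response it is 1/√(2 × 27.2) = 13.6% on 29.2 complete cases and 1/√(2 × 34) = 12.1% on 36 month-3 responders. The difference is minor, and per-visit SDs can be tabulated from all completed surveys whichever test is used.

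**Step 4: selection, one deliberately strong illustration.** Week 1 is complete and response is 80% at week 2 and month 3. In one arm only, response shifts by 1 on the log-odds scale per SD of week-1 pain. There is no true difference, and data are missing at random by construction. Baseline-adjusted complete-case analysis is off by 0.08 SD at month 3 and 0.13 SD on average over visits (0.05 and 0.08 at half that slope). As unadjusted change it is off by 0.00 at month 3, 0.15 at week 1 and 0.05 on average.

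**Step 5: blank items.** Taking 49 items from the instrument's name and random blanks at an assumed 0.1% to 0.5% per item, the share of surveys without a blank is 0.999⁴⁹ = 95% to 0.995⁴⁹ = 78%. Clustered blanks cost less.

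**The case against.** The best reply is that the harm is conditional twice over. The SAP does not say it will delete anyone, and a likelihood-based fit would not. The protocol also works to keep surveys complete, with daily reminders, payment per survey set, completion at the school and a 3-month visit. Nothing says a late survey is discarded, and the reminder in section 1.4.2 is only for participants who are upset. With response near 98%, or with the same people missing everything, there is almost nothing to recover: 36.0 against 36.5 at 90%. The selection example and the item-blank rates have no basis in the documents, and the larger biases come from a baseline-adjusted model that the SAP does not name. As a pilot, the trial mainly needs an SD, which barely changes. One sentence would close the gap.

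Much of this stands. The response rates are assumptions, independent misses show the largest gain, and the selection figures show only what could happen. But safeguards reduce missing surveys without saying how to analyse those still missing, and they do nothing for a refused item in a returned survey. The SAP also plans significance tests between groups on both aims, so who enters those tests should be fixed in advance. If the team already means a likelihood fit, the SAP still has to say so.

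**Conclusion.** The concern holds. The plan names a method whose usual form discards partial responders, while the protocol expressly lets participants skip surveys and items and no rule covers either. The loss is negligible at 98% response, small at 95% or at clustered 90%, and material below that: at 80% with independent misses, 20.5 against 32.4 equivalent participants. The size rests on assumed response rates and patterns, and the equivalent-N figures treat the covariance as known. The stated purpose of sizing a later trial is little harmed on the SD side; the cost falls on the treatment-effect estimate. The change is worth making because it is cheap, not because the pilot fails without it. No loss is assumed after a failed restoration, since measurement continues.

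**What to change.** Replace the repeated-measures GLM with a linear mixed model for repeated measures fitted by REML:
- Baseline score as covariate; group, visit, group-by-visit and baseline-by-visit terms. Covariates the team retains can enter as fixed effects.
- Unstructured covariance over the three follow-ups and Kenward-Roger degrees of freedom.
- Every randomised participant with at least one follow-up survey, analysed as randomised.
- A joint test of the group effect across the three follow-ups (3 df), with the group-by-visit term and each visit's difference reported. This keeps the planned question.

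Before unblinding, fix an item-scoring rule for OHIP-49 and the modified BPI, applied at baseline too: for example, prorate when the share of answered items is above a pre-stated level, otherwise treat the survey as missing. Report completion by arm and visit.

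The cost is SAP wording; no new data are needed. The limits are these:
- The model relies on missing at random and recovers nothing for people who miss every follow-up (0 to 8 of 40 in the range above).
- The small-sample correction is essential. In simulation (1,000 runs per case) the joint test's type I error was 4.3–5.5% with Kenward-Roger and 7.7–9.6% with an uncorrected Wald test; the complete-case exact test gave 4.0–5.4%.
- For month 3 alone it gains almost nothing over baseline-adjusted regression on everyone with that survey (simulated standard errors within 0.003).

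Potential Problems and Alternatives Strategies restarts the follow-up timeline after a replaced restoration. Which surveys then enter the model must be reconciled separately before the analysis is fully specified.

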Once enrolled, the participants will be randomly assigned to control or treatment group. The control group participants will receive the gold standard treatment for V shaped lesions - a resin modified glass ionomer (Photac-fil®). Treatment group participants will receive their V shaped lesion restoration with Biodentine™. When they receive the restoration, all treatments will follow the standard of care for their placement and polishing at the UMSoD. Participants will be assigned a random number to identify them and will be blinded as to which treatment they will receive. Participants will fill out the same OHIP-49 and BPI questionnaire via a

survey link at 1 week, 2 weeks, and 3 months post treatment. If participants complete the survey, they will receive a monetary compensation of \$10 dollars/group of surveys completed for a potential of \$40 dollars to ensure participant compliance with the survey. Surveys will be completed at recall appointments on a secure survey system maintained by the UM medical school, REDCap and data will be stored on REDCap and backed-up to a secured University of Michigan Server. Expert assessors collecting patient information will be blinded as to the treatment the participant receives. At 3 months, the patients will receive a follow up evaluation of the filling, and an evaluation of the restoration placed at the V shaped lesion. Table 1 gives a visual breakdown of the study design. The restorative materials used in this study will be placed following manufacturer's instructions.

Table 2: Study Design

Timeline	Control Group (group size: 20) Study enrollment assigned random number	Treatment Group (group size: 20) Study enrollment assigned random number
Prescreen	Oral exam, dental prophylaxis, (Part of standard of care at UMSoD) pre-screen questionnaires modified from BPI	Oral exam, dental prophylaxis, (Part of standard of care at UMSoD) pre-screen questionnaire modified from BPI
Day 1 – Baseline	OHIP-49 BPI questionnaire	OHIP-49 BPI questionnaire
Day 1 - Baseline	Treatment: PHOTACFIL®	Treatment: BIODENTINE™
Week 1 - Follow-up (survey will be emailed and should be completed within 7 days)	OHIP-49 BPI questionnaire PGIC Scale	OHIP-49 BPI questionnaire PGIC Scale
Week 2 - Follow-up (survey will be emailed and should be completed within 7 days)	OHIP-49 BPI questionnaire PGIC Scale	OHIP-49 BPI questionnaire PGIC Scale

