1.2. Sources of Materials

1.3. Data collection methods. The data obtained will be used specifically for research purposes, including: a modified Brief Pain Inventory (BPI) to reflect oral pain, OHIP-49 questionnaire and the Patient Global Impression of Change (PGIC) Scale identified only by the enrollment number that will be given to the patients. Participants will take the BPI, OHIP-49 at their first appointment, one week later, 2 weeks after the placement of the restoration and 3 months after the placement of the restoration. The PGIC survey will be given in addition to the other surveys one week after the placement of the restoration, 2 weeks after the placement of the restoration and 3 months after the placement of the restoration. Surveys will be generated on REDCap and emailed to participants to complete the survey. Daily email reminders to complete the surveys will continue until the surveys are completed.

1.4. Potential risks. Overall, potential risks associated with the participation in the study are low risk. The proposed treatments, more specifically the dental restorations, will not involve either a tooth preparation.

1.4.1. Physical. There is little likelihood of any physical risk as a result of participation in this research project. The participants will be not exposed to any physical harm. The study will be conduct at the UMSoD clinics in appropriated dental settings.

1.4.1.1 Management. Also, given the pain the patients may experience prior to the placement of the restorative material, patients may require local anesthetic during the application and finishing of the restoration. Topical anesthetic will be first applied to the gingiva and if necessary, patients may receive a carpule of 2% lidocaine HCl containing 1:100,000 epinephrine which is the standard anesthetic used in patients at the University of Michigan School of Dentistry to manage pain. The use of the local anesthesia will be limited to two carpules, 3.6ccs. This dosage is well tolerated and within the dosing considerations for patients with some associated risks with epinephrine. This amount of local anesthesia is also considered the standard of care at UMSoD. Participants will understand the minor discomfort that can be associated with EPT testing and palpation of the salivary glands.

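### Neither aim has a pre-named baseline adjustment or a promised between-arm difference with an interval, which costs a 40-person pilot precision and usable output

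*Combined protocol and SAP*

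**What the plan says.** The Statistical Analysis Plan is one paragraph covering both aims. It will use "repeated measures of general linear models (GLM) to test for significant differences between the control and treatment groups" on changes in pain (aim 1) and in oral health related quality of life (aim 2). The follow-on step is that "Significant group versus time effects will be examined graphically to determine the nature of the interaction". On covariates: "Bivariate correlations will be conducted to identify important covariates for inclusion in main statistical models (e.g. age"); age is the only example given.

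Data Collection Procedures gives four measurement times, "including prior to treatment, and 1 week, 2 weeks, and 3 months post treatment". That baseline is one of the time levels in the model is an inference from this schedule and from the word changes; the SAP does not say so. Baseline and follow-up use the same instruments: section 1.3 of Protection of Human Subjects states that "Participants will take the BPI, OHIP-49 at their first appointment", and Study Procedures that "Participants will fill out the same OHIP-49 and BPI questionnaire" after treatment.

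Power Analyses gives no effect size, SD, power or alpha. It sets 20 participants per arm in order "to generate some preliminary data for conducting a rigorous sample size analysis for a larger clinical trial".

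**The concern.** Two things are missing. First, the plan collects a baseline score for each outcome but does not commit to adjusting for it. Adjustment uses that score more efficiently than subtracting it, unless the SDs and correlation happen to make subtraction optimal. With 20 per arm, the difference can be worth several participants.

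Second, a group-by-time test over four occasions has 3 degrees of freedom and yields a p-value, not an effect. The only stated follow-up is graphical, and only for significant interactions. A sample-size calculation for the larger trial needs an estimated difference with its uncertainty, a residual SD and within-person correlations. Nothing fixes in advance which difference, adjusted for what, is carried forward.

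**Working it through.** **The plan's own figure.** The total of 40 comes with no inputs, so there is nothing to reproduce.

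**Inputs.** From the documents: n = 20 per arm, one baseline, three follow-ups. Assumed: two-sided 5% level, complete data, no restarted schedules, follow-up SD of 1, equal baseline SD unless stated, and the same correlation ρ between all visits. Triplets below are for ρ = 0.3/0.5/0.7.

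**3-month interval.** The half-width is t × √(2V/20), where V is the variance per person.
- Change from baseline: V = 2(1−ρ) = 1.40/1.00/0.60. With t(38) = 2.024, the half-width is 0.76/0.64/0.50 SD.
- Baseline-adjusted, slope estimated: V = (1−ρ²)(1 + 1/36) = 0.935/0.771/0.524. With t(37) = 2.026, the half-width is 0.62/0.56/0.46 SD.
- Adjustment is therefore about 18/12/6% narrower. Simulated variance ratios of 0.67/0.78/0.88 agree with 0.935/1.40, 0.771/1.00 and 0.524/0.60.
- Participants that change scores need to match 40 with adjustment: 40 × V(change)/V(adjusted) = 60/52/46.

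**Power for a constant effect of 0.8 SD at all three follow-ups.**
- Planned 3-df test: differences (0, 0.8, 0.8, 0.8) have mean 0.6 and sum of squared deviations 0.36 + 3 × 0.04 = 0.48. The noncentrality is (20/2) × 0.48/(1−ρ) = 6.9/9.6/16.0 on 3 and 114 df, giving 56/73/93%.
- Unadjusted 1-df change, averaged over follow-ups: V = (1+2ρ)/3 + 1 − 2ρ = 0.93/0.67/0.40, giving 72/86/97%.
- Adjusted average, slope estimated: V = [(1+2ρ)/3 − ρ²] × (1 + 1/36) = 0.456/0.428/0.319, giving about 95/96/99%.

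The first step comes from replacing 3 df by a 1-df contrast. Only the second comes from adjustment.

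**Late effect only (0, 0, 0.8 SD at the three follow-ups).** The sum of squares is again 0.48, so the planned test keeps 56/73/93%. The averaged effect is 0.8/3 = 0.27 SD, and the adjusted average has about 24/25/31% power with the slope treated as known, at most about a point less with it estimated.

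**Pain.** Let k be baseline SD divided by follow-up SD; then V(change) = 1 + k² − 2kρ.
- Participants and Table 1 require entry pain above 6, which may shrink the baseline SD. With k = 0.5 and ρ = 0.5, V(change) = 0.75 and the half-width is 0.554 against 0.563 adjusted, a loss of about 1.5%. With ρ = 0.3, V(change) = 0.95 and the half-width is 0.624 against 0.620, essentially no gain.
- With k = 1 and ρ = 0.1 or 0.2, the half-widths are 0.859 or 0.810 for change and 0.646 or 0.636 adjusted, so adjustment is about 25% or 21% narrower.

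**The correlation screen.** The SAP does not say which variable candidates are correlated with, or at what threshold. At an assumed 5% threshold with N = 40, simulation selects baseline in about 48/93/100% of trials against the single 3-month score, 77/99/100% against the follow-up average, and 99/92/72% against 3-month change.

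**The case against.** The planned test is valid under randomisation, and baseline is not ignored: it enters through the change analysis, and the screen might select it. The SAP does not forbid estimates or intervals, and the inputs for a larger trial can be computed from the data whatever test is named. An interval of ±0.56 SD is still wide. All of this stands, and it limits the point to an efficiency and reporting recommendation.

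Four stronger readings that a reader might infer are not supported.

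- **That the screen would miss baseline when correlation is low.** This holds only if baseline is screened against a single follow-up score. Against change, baseline is selected most often at low correlation. All that can be said is that selection depends on an unspecified choice.
- **That adjustment alone lifts power from 56% to about 95% at ρ = 0.3.** An unadjusted 1-df average already reaches 72%. At ρ = 0.7 adjustment adds only about 2 points to that contrast.
- **That the benefit is mainly for OHIP-49.** Only pain has an entry threshold, which points that way. But Table 2 also says "We expect an immediate elimination of pain but the impact on OHRQL will be more quantifiable if assessed over time", and follow-up pain compressed near the floor would point the other way. The documents give no SD or correlation to settle it.
- **That the averaged contrast is always better.** The planned test has far more power for an effect confined to the last visit.

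**Conclusion.** The point holds as a moderate recommendation: the analysis is valid, but it leaves precision unused and does not commit to the output that the pilot exists to produce. The reporting gap follows from the text alone. The precision gain rests on assumed correlations and SDs: about 18/12/6% narrower at 3 months with equal SDs and complete data. For pain it runs from none, or a loss of about 1–2% in width, to about 21–25% narrower. Which outcome gains more is open. The interval itself adds no precision; it makes the result usable. How evaluations are timed after a replaced restoration is a separate question, not part of this point.

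**What to change.** For pain and OHIP-49 separately, model the three follow-up scores with visit, arm, arm-by-visit and the same instrument's baseline score as a pre-named covariate that does not depend on the correlation screen. Whatever the interaction p-value, report the adjusted between-arm difference at each visit and averaged over follow-ups, each with a 95% interval, together with the residual SD and within-person correlations. The sponsor should name the main contrast for each aim before analysis, with the expected time course in mind.

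The cost is SAP wording and one degree of freedom, with no new data or participants. If the follow-up average is the main contrast, power is lost for an effect that appears only late; the visit-specific estimates would still show it.
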